### IV. Research Methods

#### A. Outcome Measure(s):

See table 1 for primary and secondary outcomes. In brief, our primary outcomes will be those related to feasibility as well as risk of 30-day all-cause hospital re-admissions. Secondary outcomes include risk of 30-day all-cause emergency department visit,

differences in readiness-to-change, and likelihood of having an alcohol metabolite (EtG) in the urine at follow-up.

*Table 1 Primary and secondary outcomes*

	Study Aim	Description	Instrument(s)
1' feasibility outcomes	1	Recruitment rate (# enrolled / month), follow-up rate, patient acceptability, adverse effects	Chart review, questionnaires
1' clinical outcome	2	Risk of 30-day all-cause hospital re-admissions	Chart review
2' clinical outcomes	2	Risk of 30-day all-cause ED visits	Chart review
	2	Within-subject difference in readiness-to-change 	Questionnaire
	2	Laboratory(+) for alcohol at SUDS	Urine EtG
	2	Percent of binge drinking days  since discharge	Questionnaire

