### ***Data Collection***

Data will be primarily collected at four time-points (Table 4). Data will be entered by staff into a REDCap database on tablet computers in the hospital and at SUDS clinic. Data collected at enrollment will primarily be descriptive, including demographics, recent drinking history, readiness to change, and various contributing factors to drinking. Immediately after intervention, vital signs,

symptoms, and acceptability will be recorded. Data collected on post-discharge arrival to SUDS clinic will include most 2' clinical outcomes. We will obtain re-admission rate (1' clinical outcome) through chart review, conducted by research team members at 30-days post-discharge.

Table 4 Patient flow and data collection points

Step	Who	Notes	Data collected – staff entered
Patient identified on consult list	ACS	Quick screen that meets inclusion criteria	
↓			
Addiction consult performed	ACS	Evaluation, withdrawal management, medication (though if patient consents to study, will not be prescribed an addiction medication at discharge), brief therapy, referrals, disease screening/harm reduction	
↓			
Screen, consent, randomization	ACS	Formal screen to identify any exclusion criteria. Simple randomization by algorithm	
 
• E-Consent (should include consent to see records in “care everywhere” – some hospitals require permission – when checking for ED visits and re-admissions)
 
• Screening documentation (inclusion and exclusion criteria)
 
• Alcohol-related admissions in last 12 months (date, location, top 3 diagnoses)
 
• Assigned group
 

↓			
Baseline data, referral to SUDS [data collection point #1]	ToD	ToD collects baseline data first, then performs “biopsychosocial intake” and sets up SUDS appointment within 1 week of discharge.  Discharge date is not always predictable;	
 
• Demographics
 
• Baseline clinical data
 
• Depression symptoms baseline (PHQ9 2 wks)
 
• Drinking History 7-days prior to admission (TLFB)
 
• Readiness to change (SOCRATES-8A)
 
• ACE Questionnaire
 

		ACS to review active hospitalized research participants and contact ToD/update date in RedCap as needed.	
↓			

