Intervention administered [data collection point #2]	RN, ACS	
For 'linkage-alone' group, data to be entered following consult.
 
For NTX group, intervention administered prior to discharge (could be same day as consent). Vitals immediately preceding and 40 min post- injection. Data collected after administration.
 
For KET group, intervention administered prior to discharge (could be same day as consent), though should have no food for at least 3 hours (~50% gastric emptying). Vitals immediately preceding, after completion, and 2 hours following end of intervention.
	
 
Vital signs (HR, BP, O2): linkage-alone group- baseline only, recorded after consult. NTX group- baseline, 40 min after administration. KET group- baseline, end of administration (~40min), 2 hours after end of administration.
 
Most recent AST, ALT
 
UDS-5 data
 
[for KET] Dissociative symptoms (CADSS) after administration (40 min)
 
[for NTX and KET] Acceptability of intervention (10-point Likert) after administration
 
[for NTX and KET] Readiness to change (SOCRATES-8A) after administration (40 min)
 
 
ORDER: CMP (if not already obtained), UDS-5 (if not already obtained)
 
ORDER in discharge orders (outpatient): CMP, UDS-5, urine EtG (if not already ordered)

↓			
Presentation to SUDS, data entered, contingency management reward administered [data collection point #3]	SUDS staff	
Upon presentation, staff to collect study data. After completion, will receive contingency management reward.
 
Then patient to complete standard intake/follow-up visit, if willing.
	
 
Drinking History since discharge (TLFB since discharge)
 
Depression symptoms (PHQ9 modified to read "since discharge.")
 
Readiness to change (SOCRATES-8A)
 
[for KET] Dissociative symptoms (CADSS)
 
Adverse Events (Modified PRISE)
 
Acceptability of intervention (10-point Likert)
 

		Staff to instruct patient to present to the clinic laboratory (e.g. pav G) for CMP after the visit.	
 
Contingency management feedback (10-point Likert, open ended)
 

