#### **D. Description, Risks and Justification of Procedures and Data Collection Tools:**

*Table 5 Overview of risks and justifications of procedures and data collection tools*

Procedure/Tool	Description, Risks	Justification
Injection of IM medication (naltrexone)	Risks include minimal pain and discomfort at the injection site which will occur on the lateral thigh or the buttock. One study suggested that the discomfort of an injection itself deterred a large number of participants.  If that is the case for our study, this decision will be honored with no repercussion aside from not enrolling in the study. More serious risks such as infection, blood clot, bleeding and/or allergic reaction are rare.	These risks are justifiable as there is very little risk of serious or permanent harm, and potential benefits in terms of preventing the consequences of heavy drinking are almost certainly greater.
Medication-related risks of naltrexone	Risk of opioid withdrawal if the patient is taking opioids concurrently (an exclusion criteria); Liver injury can be seen, but is usually mild and self-limiting. Patients with AST/ALT >5x ULN, hepatic failure, or decompensated cirrhosis will be excluded. Nausea, sleepiness and headache are the other most common medication side effects.	These risks are justifiable as there is very little risk of serious or permanent harm, and potential benefits in terms of preventing the consequences of heavy drinking. It is a single dose which limits exposure.
Medication-related risks of ketamine	Risk of unpleasant dissociative symptoms, delirium, hallucinations; high blood pressure which could lead to adverse cardiac events if patients are not screened carefully; initiation of ketamine abuse after discharge.	These risks are justifiable as there is very little risk of serious or permanent harm, and potential benefits in terms of preventing the consequences of heavy drinking. It is a single dose which limits exposure. Patients who experienced delirium during hospital stay will be excluded. Patients with known cardiovascular disease will be excluded. The most recent randomized trial using ketamine found no initiation of ketamine “abuse” following administration. 

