#### **F. Data Analysis Plan:**

Participants’ demographic and baseline clinical data will be tabulated, and differences between groups will be assessed using a Fisher’s Exact Test for categorical variables and a two-sample t-test for continuous variables. These tests

will help evaluate the effectiveness of randomization. Feasibility outcomes (Aim 1) such as adverse events and acceptability (Likert scale) will be compared for each group using a Fisher's Exact Test and Wilcoxon-Mann-Whitney Test, respectively. Overall recruitment rate and follow-up rate will be tallied at the conclusion of data collection.

For Aim 2, all-cause hospital re-admission within 30-days of discharge will be recorded as a binary outcome. Rates of the two medication intervention groups (XR naltrexone or IV ketamine) will be compared against the group that received enhanced linkage to care alone.

This pilot study may not be sufficiently powered for robust hypothesis testing. By one crude estimate, we could have approximately 80% power to detect a difference between a medication group and the linkage-alone group with about 60 participants assuming a re-admission rate is 25% vs 15%. A larger effect size would increase our power and/or reduce the number of participants required. Regardless, this will provide parameter estimates that can inform a future sample size calculation in a larger effectiveness trial.

For further descriptive purposes, a secondary utilization outcome is risk of 30-day all-cause ED visits. This will be evaluated in a similar manner as hospital re-admissions. Additionally, we are interested in the within-subject difference in readiness-to-change. For those who follow-up, a mean of pre/post differences will be calculated, and a paired t-test will be used to determine if the null hypothesis ( $H_0$ : difference = 0) can be rejected. Drinking behavior will be measured using the Timeline Follow Back method. Binge drinking will be defined as 5+ drinks for men, 4+ for women, and the proportion of binge drinking days since discharge will be calculated for each group. Proportions of positive urine ethyl glucuronide (EtG) will also be tabulated for each group.

Data will be analyzed in SAS.

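### The modified PRISE and the CADSS have no pre-treatment measurement and no new-or-worse rule, so per-arm adverse-event rates can include pre-existing symptoms and the ketamine CADSS cannot be read as a change

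*Combined protocol and SAP*

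**What the plan says.** Table 1 (section IV.A) gives the primary feasibility outcomes as "Recruitment rate (# enrolled / month), follow-up rate, patient acceptability, adverse effects". The Data Analysis Plan then says that "Feasibility outcomes (Aim 1) such as adverse events and acceptability (Likert scale" will be compared between groups, adverse events by Fisher's exact test. It gives no definition of a treatment-emergent event, no attribution rule and no use of a baseline.

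Table 4 (section IV.C) sets the timing of the instruments:

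- **Modified PRISE.** Listed once, at data collection point #3 (the SUDS visit), as "Adverse Events (Modified PRISE". It carries no arm label, so it applies to all three arms.
- **CADSS.** Listed at point #2 as "for KET] Dissociative symptoms (CADSS) after administration (40 min" and at point #3 as "for KET] Dissociative symptoms (CADSS". Both entries are for the ketamine arm only.
- **Point #1 (baseline).** Demographics, unspecified baseline clinical data, "Depression symptoms baseline (PHQ9 2 wks", TLFB, SOCRATES-8A and ACE. Neither PRISE nor CADSS is there.
- **Vital signs.** Taken before dosing in both medication arms; for ketamine, "Vitals immediately preceding, after completion, and 2 hours following end of intervention".

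Table 5 (section IV.D) says of naltrexone, after opioid withdrawal and liver injury, "Nausea, sleepiness and headache are the other most common medication side effects". For ketamine it names dissociation, delirium and hallucinations among the risks.

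**The concern.** PHQ-9, TLFB, SOCRATES-8A and vital signs all have a value before treatment. PRISE and CADSS do not, and no reason is given.

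Nausea, sleepiness and headache are non-specific. The participants are inpatients with alcohol use disorder, and Table 3 excludes only active moderate or severe withdrawal, so patients with mild withdrawal can enter. A patient with one of these symptoms before dosing, who still has it at SUDS, looks the same on the form as a patient in whom the drug caused it.

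Two readings suffer. First, the adverse-event rate in each arm, which the pilot is meant to hand to a larger trial, may be too high as an estimate of what the drug does. Second, a ketamine-arm CADSS score cannot be turned into a change, and a raised score at SUDS could be a lasting effect or the patient's usual state. A baseline not taken before dosing cannot be recovered later.

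**Working it through.** The documents give no figure for the adverse-event comparison, so there is none to reproduce. What follows is an illustration on assumed rates.

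**Inputs from the documents.** Total 45 to 60 in three arms by simple randomisation. With equal arms (the ratio is not stated) that is 45/3 = 15 to 60/3 = 20 per arm. PRISE comes only from patients who attend SUDS, so fewer may be assessed; 10 per arm is included for that reason.

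**Assumptions.** A fraction b of every arm has a given symptom before dosing and still has it at SUDS. The drug causes it in 30% of the rest. No other new symptoms arise. The test is two-sided Fisher at 0.05; the plan states no level.

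**Any-symptom count (no baseline available).**
- Control rate = b
- Drug rate = 1 − (1 − b)(1 − 0.30)
- Difference = 0.30(1 − b)

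**New-symptom count (baseline available).**
- Control rate = 0
- Drug rate = 0.30(1 − b), all randomised and assessed patients in the denominator
- Difference = 0.30(1 − b), the same as above

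So a baseline does not enlarge the expected difference. It removes the background from each arm's rate and from the variance. For b = 20%:

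- Any symptom: control 20%, drug 1 − 0.80 × 0.70 = 44%, difference 24 points, SE = √[(0.44 × 0.56 + 0.20 × 0.80)/20] = 14.3 points.
- New symptom: control 0%, drug 24%, difference 24 points, SE = √[0.24 × 0.76/20] = 9.6 points.

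Exact Fisher power, by enumerating all outcomes (any symptom → new symptom):

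| Assessed per arm | b = 20% | b = 50% | b = 70% |
|---|---|---|---|
| 20 | 27% → 54% | 9% → 17% | 5.4% → 2.9% |
| 15 | 16% → 28% | 5.7% → 6.2% | 3.5% → 0.8% |
| 10 | 8.3% → 6.7% | 3.4% → 1.0% | 1.9% → 0.1% |

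The expected difference is 24, 15 and 9 points in the three columns. The gain is real at low background with 15 to 20 assessed, and negligible or reversed elsewhere. The b = 70% column counts only new symptoms; counting worsening as well could change it, but the documents give nothing to model that.

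**False positives.** With no drug effect and equal b in both arms, the any-symptom Fisher test with 20 per arm rejects in 2.0% to 2.5% of trials at b = 20%, 50% and 70%. Shared background symptoms do not create a false excess on drug.

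**CADSS.** No arithmetic applies. Scores exist only after the infusion and only in one arm, so there is neither a within-patient change nor a control value.

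**The case against.** The strongest reply is that the trial already has the right control. The linkage-alone arm is randomised and completes the same PRISE, so pre-existing symptoms are balanced in expectation. That stands. A reader might infer that the drugs will be blamed for withdrawal symptoms; the documents do not support it, and the false-positive rates above agree. A reader might also stress chance imbalance: at b = 50% and 20 per arm the SE from background alone is √(2 × 0.25/20) = 15.8 points, or about ±31 points at 1.96 SE. That is ordinary sampling error, which Fisher's test already allows for.

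Three further replies also narrow the point:

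- **Wording unknown.** The content and recall window of the modified PRISE are not shown. The PHQ-9 at the same visit was reworded to cover the period since discharge, and the PRISE may have been too. To say that old symptoms *are* counted would be inference; they *can* be.
- **CADSS is separate.** It is ketamine-only and is not named in the Fisher comparison, so it cannot distort the comparison between arms. Only the within-arm reading is limited.
- **Persistence.** Inpatient symptoms may have gone by SUDS, which is scheduled within 7 days of discharge. Moderate or severe withdrawal, active delirium and active psychosis are excluded. A new-or-worse rule could then discard a true drug effect in someone who was nauseated on the ward.

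It is also fair to note that Table 1 lists chart review beside questionnaires, that the Data Collection text mentions symptoms recorded just after the intervention, and that point #1 includes unspecified clinical data. None of these is a stated pre-dose symptom checklist that matches the PRISE.

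**Conclusion.** The point holds in a limited form, as a cheap improvement to a pilot. Neither instrument has a pre-treatment value, and the plan has no new-or-worse definition for a primary feasibility outcome. Unless the PRISE wording already handles it, per-arm rates can include background symptoms: in the illustration at b = 20%, the drug arm shows 44% where 24% is new. The ketamine CADSS cannot be reported as a change.

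The comparison with linkage-alone is not biased against the drugs. It loses precision mainly when background symptoms are uncommon and 15 to 20 per arm are assessed. All sizes rest on the assumed background rate, the 30% drug effect and full persistence of baseline symptoms to SUDS; new background symptoms after discharge would shrink the gain.

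**What to change.** In Table 4:

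- Add the modified PRISE at data collection point #1 in all three arms, before any dosing, and state its wording and recall window.
- In the ketamine arm, add a CADSS alongside the vital signs already taken just before the infusion. A further CADSS at the existing 2-hour vitals check is optional; it would describe recovery and is not needed for a baseline.

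In the Data Analysis Plan, add that PRISE results will be reported by arm in two ways, any symptom at SUDS and any symptom new or worse than baseline. State also that CADSS change from the pre-infusion score will be reported as a within-arm description.

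The cost is a few minutes of respondent time at contacts already scheduled, plus a short addition to the analysis text. Symptoms on the ward may raise the baseline and hide some drug-caused symptoms, which is why both rates should be shown. A baseline will not remove symptoms caused by drinking after discharge.

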30-day chart review [data collection point #4]	Research staff	Should check encounters tab as well as “care everywhere” for Denver Metro region.	
 
Admissions (up to 5) within 30 days of discharge date (date, location, up to top 3 main diagnoses based on documentation available).
 
ED visits (up to 5) within 30 days of discharge date (date, location, up to top 3 main diagnoses based on documentation available).
 
AST, ALT obtained at SUDS f/u (if available)
 
Urine EtG obtained at SUDS f/u (if available)
 

Screening: The addiction consult team will attempt to screen patients meeting the inclusion criteria during inpatient admission. We anticipate 10 patients will meet inclusion criteria weekly. They will be assessed for clear exclusion criteria documented in the chart, and if none are noted the patient will be asked if they would like to join the study and complete the screening. If still no exclusion criteria are met and the patient expresses interest, they will be engaged in informed consent. The primary team will be notified by the addiction medicine team. Each combined process of screening and consent is anticipated to require 15 minutes at the end of a typical consultation. The screening window is anticipated to last 5 months.

Randomization: Patients will undergo a simple randomization algorithm to one of three arms.

Intervention:

- **Arm 1:** Receive a single dose of XR naltrexone (380mg) prior to discharge.
- **Arm 2:** Receive a single infusion of IV ketamine (0.5 mg/kg over 40 minutes) prior to discharge.
- **Arm 3:** No single-dose medication
- *All groups will receive enhanced linkage to care that includes contingency management, initiation of biopsychosocial intake, and appointment scheduling. This aspect alone surpasses the current standard of care.*

Contingency Management: Patients will receive a debit card prior to discharge from the hospital. We will utilize a pre-existing system - ClinCard by Greenphire. Participants will receive \$10 upon completion of baseline data, and \$20 upon completion of follow-up data (at SUDS clinic).

Follow up: Patients will be assigned a follow-up within 7 days of discharge at the outpatient addiction clinic (Denver Health SUDS clinic in pavilion K).

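### The SUDS step of Table 4 does not secure the urine EtG specimen before the reward is paid, so the proportion positive may come from a self-selected subset of attenders

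*Combined protocol and SAP*

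**What the plan says.** Section IV.A describes the outcome as the "likelihood of having an alcohol metabolite (EtG) in the urine at follow-up". Table 1 lists it as a secondary clinical outcome under Aim 2, "Laboratory(+) for alcohol at SUDS", with urine EtG as the instrument. The other drinking outcome in that table, the percentage of binge days, comes from a questionnaire.

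Table 4 (section IV.C) covers EtG in three places:

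- **Data collection point #2 (hospital):** "ORDER in discharge orders (outpatient): CMP, UDS-5, urine EtG (if not already ordered".
- **Data collection point #3 (SUDS visit):** the data column lists questionnaires, adverse events and feedback items, with no urine specimen. The notes give the order of events. Study data come first. On the reward they say: "After completion, will receive contingency management reward". The standard clinic visit follows if the patient is willing. Last comes the laboratory: "Staff to instruct patient to present to the clinic laboratory (e.g. pav G) for CMP after the visit".
- **Data collection point #4 (30-day chart review):** "Urine EtG obtained at SUDS f/u (if available").

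The Contingency Management paragraph releases the $20 "upon completion of follow-up data (at SUDS clinic"). The Data Analysis Plan (section IV.F) says: "Proportions of positive urine ethyl glucuronide (EtG) will also be tabulated for each group". It states neither a denominator nor how missing results are treated.

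**The concern.** The outcome is tied to the SUDS visit, but the step describing that visit does not ensure that a specimen is obtained there. By the time laboratory testing is mentioned, the patient has answered the questionnaires, has been paid, and may have left, because the remaining visit is optional. The instruction then names one of the three tests ordered at discharge, and not the one that supplies a study outcome.

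This loss arises among patients who did attend, so it is separate from non-attendance. Section IV.E recognizes low SUDS attendance and offers contingency management as the response. An incentive paid on completing the clinic data cannot reach a loss that occurs after payment.

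At stake is how the EtG table can be read. If drinkers and abstainers are tested at different rates, the proportion positive does not describe attenders. A low figure could not then be told apart from drinkers leaving without a test, and there would be no sound objective check on self-reported drinking. The pilot is meant to inform a larger trial, so a collection procedure that loses specimens would be carried forward with it.

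**Working it through.** **1. Trace the written sequence.** Three attenders, each following Table 4 as it stands:

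- One completes the study data, is paid, and declines the standard visit. Nothing in the step obtains urine, so unless the clinic takes it by a route that the table does not describe, there is no EtG result.
- One stays and goes to the laboratory after being told about CMP. The discharge order also covers EtG and UDS-5, so EtG may well be run, provided the laboratory acts on that order.
- One stays for the visit but skips the laboratory. No payment is lost, and on the laboratory route there is no EtG result.

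The SUDS clinic is in pavilion K, and the laboratory is given, as an example, in pavilion G, so the laboratory may be a separate trip.

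**2. Is there a plan figure to reproduce?** None for EtG: no expected rate, sample size or completion rate is given. The nearest is the historical addiction-clinic follow-up, 2 of 17: 2/17 = 11.8%, which agrees with section II. It predates the planned incentive.

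**3. What unequal completion would do.** Let p be the true proportion positive among attenders, d the completion of testing in drinking attenders, and a the completion in abstinent attenders. All three are assumptions.

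Observed proportion = p·d / [p·d + (1 − p)·a]

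With a = 0.80:

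| p | d | Calculation | Observed |
|---|---|---|---|
| 0.60 | 0.30 | 0.18/(0.18 + 0.32) | 36% |
| 0.60 | 0.50 | 0.30/(0.30 + 0.32) | 48% |
| 0.60 | 0.70 | 0.42/(0.42 + 0.32) | 57% |
| 0.60 | 0.80 | 0.48/(0.48 + 0.32) | 60% (no bias) |
| 0.40 | 0.30 | 0.12/(0.12 + 0.48) | 20% |
| 0.40 | 0.50 | 0.20/(0.20 + 0.48) | 29% |
| 0.40 | 0.70 | 0.28/(0.28 + 0.48) | 37% |
| 0.40 | 0.80 | 0.32/(0.32 + 0.48) | 40% (no bias) |

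In the second row, 0.30 + 0.32 = 62% of attenders have a result, and the observed rate is 12 points low. Reversing the two completion rates (d = 0.80, a = 0.50) gives 0.48/(0.48 + 0.20) = 71%, which is 11 points high. The sign therefore depends on who skips.

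**4. How many results would remain.** Randomizing 45–60 patients to three arms gives 15–20 per arm on average. Expected results per arm = n × attendance × completion among attenders:

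- 11.8% attendance (historical), full completion: 15 × 0.118 = 1.8 to 20 × 0.118 = 2.4.
- 50% attendance (assumed), full completion: 7.5 to 10.
- 50% attendance, 62% completion: 7.5 × 0.62 = 4.7 to 10 × 0.62 = 6.2.
- 74% attendance (the control-group figure that section II cites from a ketamine trial), 62% completion: 11.1 × 0.62 = 6.9 to 14.8 × 0.62 = 9.2.

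With 5 or 6 results in an arm, one specimen more or less is 17 to 20 percentage points (1/6 to 1/5).

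**The case against.** The strongest reply is that Table 4 does not exclude a urine specimen at SUDS. The data column covers what staff enter. CMP, for which patients are expressly sent, is missing from the same list, and follow-up AST and ALT are retrieved at chart review in the same way as EtG. Absence from the list is therefore weak evidence. Table 1 places the outcome at SUDS, so the text also permits urine taken in clinic, with only the CMP needing the laboratory. This stands. A reader might infer that the clinic takes no urine, or that the laboratory visit is for CMP alone. The documents say neither, and the discharge order points the other way for anyone who reaches the laboratory.

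A reader might also infer that positivity is biased downward, or that the arms will differ spuriously. That is not established either. Payment does not depend on abstinence, no penalty attaches to a positive result, and a patient told only about CMP has less reason to avoid the laboratory on account of drinking. The completion rates above are invented for illustration. An artificial gap between arms of 57% − 36% = 21 points would need drinkers' completion of 70% in one arm and 30% in another, and apart from the open-label design nothing in the documents suggests such a gap.

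Finally, EtG is a secondary outcome, tabulated without a planned test, in a trial whose main aim is feasibility. At 5 to 6 results per arm the standard error near 48% is √(0.484 × 0.516/6) = 20 points to √(0.484 × 0.516/5) = 22 points, more than the illustrated 12-point bias. That limits the consequence, but it does not excuse a procedure that can lose specimens from patients already in the clinic.

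**Conclusion.** The concern holds as a gap in procedure and reporting. The outcome definition, the discharge order, the SUDS step and the laboratory instruction do not fit together. Followed as written, they allow a paid attender to leave without an EtG result, and the analysis plan does not say over whom the proportion is taken. The result may therefore describe a self-selected subset of attenders.

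Neither the direction nor the size of any bias can be derived from the documents. If drinkers are tested less often, positivity is understated: for example, 48% observed for a true 60%, under assumed completion of 50% in drinking and 80% in abstinent attenders. If completion is equal there is no bias, only fewer results. The point does not touch the primary clinical outcome, re-admission, which needs no SUDS data. The change should be made because it is cheap and cannot be made after the visits have taken place.

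**What to change.** - **Table 4, data collection point #3:** list the urine EtG specimen as a study item, requested on arrival, before the reward and the optional visit. State where it is taken.
- **Staff instruction in the same step:** name urine EtG, UDS-5 and CMP, so that it matches the discharge order.
- **Section IV.F:** report by arm the number with an EtG result beside the numbers attending SUDS and the numbers randomized, and label the proportion positive as being among those tested.

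Making the $20 conditional on giving a specimen, whatever its result, is optional. It would strengthen completion, but it changes an incentive given to all arms and could deter some patients from attending, and follow-up rate is a primary feasibility outcome. Asking for the specimen early and reporting the denominators achieves most of the gain without it.

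The cost is a wording change in Table 4, one line in IV.F, and a few more minutes before payment. The test is already ordered. If urine can be taken only at the laboratory, the trip there would have to come before the reward, which is a larger burden and should be weighed when choosing the place.
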